4.1.7 Organ Function Requirements

4.1.7.1 Adequate Bone Marrow Function Defined as:

- a. For patients with solid tumors without known bone marrow involvement:
  - Peripheral absolute neutrophil count (ANC)  $\geq 1000/\text{mm}^3$
  - Platelet count  $\geq 100,000/\text{mm}^3$  (transfusion independent, defined as not receiving platelet transfusions for at least 7 days prior to enrollment)
  - Hemoglobin  $\geq 8.0$  g/dL at baseline (may receive RBC transfusions)
- b. Patients with known bone marrow metastatic disease will be eligible for study provided they meet the blood counts in 4.1.7.1.a (may receive platelet or pRBC transfusions provided they are not known to be refractory to red cell or platelet transfusions). These patients will not be evaluable for hematologic toxicity.

4.1.7.2 Adequate Renal Function Defined as:

- Creatinine clearance or radioisotope GFR  $\geq 70\text{ml}/\text{min}/1.73 \text{ m}^2$  or
- A serum creatinine based on age/gender as follows:

Age	Maximum Serum Creatinine (mg/dL)	
	Male	Female
1 to < 2 years	0.6	0.6
2 to < 6 years	0.8	0.8
6 to < 10 years	1	1
10 to < 13 years	1.2	1.2
13 to < 16 years	1.5	1.4
$\geq 16$ years	1.7	1.4

The threshold creatinine values in this Table were derived from the Schwartz formula for estimating GFR (Schwartz et al. J. Peds, 106:522, 1985) utilizing child length and stature data published by the CDC.

4.1.7.3 Adequate Liver Function Defined as:

- Bilirubin (sum of conjugated + unconjugated)  $\leq 1.5$  x upper limit

- of normal (ULN) for age
- SGPT (ALT)  $\leq$  135 U/L. (For the purpose of this study, the ULN for SGPT is 45 U/L.)
- Serum albumin  $\geq$  2 g/dL

4.1.7.4 Adequate Cardiac Function Defined as:

- QTc interval  $\leq$  480 milliseconds

4.1.7.5 Adequate Pulmonary Function Defined as:

- Pulse oximetry  $>$  94% on room air if there is clinical indication for determination (e.g. dyspnea at rest).

4.1.8 Patients must be able to swallow intact tablets.

4.1.9 Informed Consent: All patients and/or their parents or legally authorized representatives must sign a written informed consent. Assent, when appropriate, will be obtained according to institutional guidelines.

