**5.4.1 Non-Hematological Dose-Limiting Toxicity**

- 5.4.1.1 Any Grade 3 or greater non-hematological toxicity attributable to the investigational drug with the specific exclusion of:
- Grade 3 nausea and vomiting of < 3 days duration
  - Grade 3 liver enzyme elevation, including ALT/AST/GGT that returns to

levels that meet initial eligibility criteria or baseline within 7 days. See [Section 6.3](#), and [Appendix XI](#) for values that represent thresholds between CTCAE grades.

Note: For the purposes of this study the ULN for ALT is defined as 45 U/L regardless of baseline.

- Grade 3 or 4 fever < 5 days duration.
- Grade 3 infection < 5 days duration.
- Grade 3 hypophosphatemia, hypokalemia, hypocalcemia or hypomagnesemia responsive to supplementation

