**6.3 Dose Modifications for Hepatic Adverse Events**

- 6.3.1 If a patient experiences Grade 3 ALT/AST/GGT, treatment will be held. If toxicity resolves to meet eligibility criteria within 7 days, the drug may be resumed at the same dose. Grade 3 ALT/AST/GGT that persists  $\geq 7$  days will be considered dose-limiting and require dose modification per [Section 6.2](#). See [Appendix XI](#) for values that represent thresholds between CTCAE grades.
- 6.3.2 If a patient experiences Grade 4 ALT/AST/GGT, the patient must be removed from protocol therapy. See [Appendix XI](#) for values that represent thresholds between CTCAE grades.

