**8.0 EVALUATIONS/MATERIAL AND DATA TO BE ACCESSIONED**

**8.1 Required Clinical, Laboratory and Disease Evaluation**

All clinical and laboratory studies to determine eligibility must be performed within 7 days prior to enrollment unless otherwise indicated. Laboratory values used to assess eligibility (see [Section 4.0](#)) must be no older than seven (7) days at the start of therapy. Laboratory tests need **not** be repeated if therapy starts **within** seven (7) days of obtaining labs to assess eligibility. If a post-enrollment lab value is outside the limits of eligibility, or laboratory values are older than 7 days, then the following laboratory evaluations must be re-checked within 48 hours prior to initiating therapy: CBC with differential, bilirubin, ALT (SGPT) and serum creatinine. If the recheck is outside the limits of eligibility, the patient may not receive protocol therapy and will be considered off protocol therapy. Imaging studies, bone marrow aspirate and/or biopsy, must be obtained within 14 days prior to start of protocol therapy (repeat the tumor imaging if necessary).

STUDIES TO BE OBTAINED	Pre-Study	During Cycle 1	Prior to Subsequent Cycles^
History	X	Weekly	X
Physical Exam with vital signs	X	Weekly	X
Neurologic Exam	X		
Height, weight, BSA	X		X
Performance Status	X		
Pregnancy Test 	X		
CBC, differential, platelets	X	Twice Weekly (every 3 to 4 days) 	Weekly 
Urinalysis	X		
Electrolytes including Ca ++ , PO 4 , Mg ++	X	Weekly	X
Creatinine, ALT, bilirubin	X	Weekly	X
Albumin	X		X
Tumor Disease Evaluation 4-A, 4-B,	X		Every other cycle x 3 then q 3 cycles 
Bone Marrow Aspirate and/or biopsy 	X 		
EKG	X		
Ophthalmologic exam 	X	X	Every cycle during the first 4 cycles of treatment, then every 3 cycles afterward 
Plain radiograph tibial growth plate (Bone X-Ray Tests) 	X		Prior to cycles 2, 5 and every 6 months
Medication Diary 		Weekly	X
Pharmacokinetics (optional) 			
Circulating Tumor DNA (ctDNA- optional) 			Cycle 5, Day 1 and (for patients receiving ≥ 5 cycles

			only) at end of Protocol Therapy OR disease progression
--	--	--	---

- ^ Studies may be obtained within 72 hours prior to the start of the subsequent cycle.

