**APPENDIX XI TOXICITY-SPECIFIC GRADING**

Bilirubin

Grade 1:	$\leq 1.5 \times \text{ULN}$
Grade 2:	$> 1.5 \times - 3 \times \text{ULN}$
Grade 3:	$> 3 \times - 10 \times \text{ULN}$
Grade 4:	$> 10 \times \text{ULN}$

ALT: For the purpose of this study, the ULN for ALT is 45 U/L regardless of baseline.

Grade 1:	$\leq 135 \text{ U/L}$
Grade 2:	136 U/L - 225 U/L
Grade 3:	226 U/L - 900 U/L
Grade 4:	$> 900 \text{ U/L}$

AST: For the purpose of this study, the ULN for AST is 50 U/L regardless of baseline.

Grade 1:	$\leq 150 \text{ U/L}$
Grade 2:	151 U/L - 250 U/L
Grade 3:	251 U/L - 1000 U/L
Grade 4:	$> 1000 \text{ U/L}$

GGT:

Grade 1:	$> \text{ULN} - 2.5 \times \text{ULN}$
Grade 2:	$> 2.5 \times \text{ULN} - 5 \times \text{ULN}$
Grade 3:	$> 5 \times \text{ULN} - 20 \times \text{ULN}$
Grade 4:	$> 20 \times \text{ULN}$

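### AST and GGT appear in the hold, removal and DLT-exclusion rules, but are not in the required laboratory schedule and have no defined recovery reference

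*Combined protocol and SAP*

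**What the plan says.** Three places treat ALT, AST and GGT as a set.

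- Section 6.3.1: "If a patient experiences Grade 3 ALT/AST/GGT, treatment will be held". It then says: "If toxicity resolves to meet eligibility criteria within 7 days, the drug may be resumed at the same dose". A Grade 3 elevation lasting 7 days or more is dose-limiting and passes to Section 6.2.
- Section 6.3.2: "If a patient experiences Grade 4 ALT/AST/GGT, the patient must be removed from protocol therapy".
- Section 5.4.1.1 counts any attributable non-hematological toxicity of Grade 3 or worse as a DLT. Its list of exclusions includes "Grade 3 liver enzyme elevation, including ALT/AST/GGT that returns to" eligibility levels or baseline within 7 days.

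Appendix XI gives each enzyme its own cut-offs and sets a study-specific limit for AST: "AST: For the purpose of this study, the ULN for AST is 50 U/L regardless of baseline".

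The assessment schedule is narrower. The liver enzyme row of the Section 8.1 table is "Creatinine, ALT, bilirubin" (pre-study, weekly in Cycle 1, before each later cycle), and albumin has its own row. The footnotes add no enzyme. Item e of the Cycle 1 map in Appendix V has the same content. The re-check before first dose covers "CBC with differential, bilirubin, ALT (SGPT) and serum creatinine". Eligibility (Section 4.1.7.3) sets limits for bilirubin, ALT and albumin only. The ALT limit is 135 U/L, with the note "For the purpose of this study, the ULN for SGPT is 45 U/L".

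**The concern.** A rule that acts on a laboratory value needs that value to be collected. A site that follows the required schedule exactly would never obtain an AST or GGT result, so it could never trigger the AST or GGT part of Section 6.3. Where those tests are done, they are done at the site's discretion.

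Two things are at stake. The first is ascertainment. Tolerability is secondary aim 1.2.2, Section 2.3.1 reports no prior experience in children, and Section 11.4 tabulates incidence by toxicity type and grade. For AST and GGT, that incidence would depend partly on who was tested. The second is application of the rule. Even with a Grade 3 AST or GGT in hand, the protocol does not give the value against which recovery is judged.

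**Working it through.** The plan states no statistical figure on this point. The check sets the passages side by side.

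**1. Is the grading table sound?** Appendix XI uses 3, 5 and 20 times the upper limit of normal (ULN) for the transaminases.
- ALT, ULN 45: 3 × 45 = 135; 5 × 45 = 225; 20 × 45 = 900 U/L.
- AST, ULN 50: 3 × 50 = 150; 5 × 50 = 250; 20 × 50 = 1000 U/L.

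These match the printed cut-offs. The mismatch is not in the grading; it lies between the rules and the schedule.

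**2. Rules against schedule.**

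| | ALT | AST | GGT |
|---|---|---|---|
| Hold at Grade 3, removal at Grade 4 (6.3) | yes | yes | yes |
| Grade 3 range (Appendix XI) | 226–900 U/L | 251–1000 U/L | >5 to 20 × ULN |
| Grade 4 (Appendix XI) | >900 U/L | >1000 U/L | >20 × ULN |
| Eligibility limit (4.1.7.3) | 135 U/L | none | none |
| Required at baseline (8.1) | yes | no | no |
| Required on treatment (8.1) | weekly in Cycle 1, then before each cycle | no | no |

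One of three enzymes is scheduled. In the Cycle 1 map, item e falls on Days 8, 15, 22 and 28. With the pre-study draw, that is 1 + 4 = 5 required ALT results by the end of Cycle 1, against 0 for AST and 0 for GGT.

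**3. What happens once a Grade 3 AST or GGT is found.** Section 6.3.1 judges recovery by return to eligibility criteria. Section 4.1.7.3 supplies that value for ALT and for neither of the others. Sections 5.4.1.1 and 6.2.1 also accept return to baseline, but no baseline AST or GGT is required, so that reference may not exist. Several outcomes hang on this recovery test: DLT or not (5.4.1.1), same or reduced dose (6.3.1, 6.2.1), and removal if unresolved at 14 days (6.2.2).

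**4. Effect on the toxicity tables.** Section 11.6 evaluates toxicity in all eligible patients who receive at least one dose, tested or not. Let p be the true incidence, f the fraction of patients tested, and N the number treated. If testing is unrelated to the result and an untested patient contributes no event, the expected count is N × p × f. The documents do not give f. With N = 20 and, for illustration, p at the top of the agent table's category for AST increased (20%, any grade, from that table's 417 patients), the count is 20 × 0.20 × f = 4f. It runs from 0 (no one tested) to 4 (everyone tested). Grade 3 and 4 events, on which Section 6.3 acts, would be fewer.

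**5. How far the agent information supports each enzyme.** AST increased is in the Section 9.1.2 table of events possibly related to erdafitinib. GGT increased is not; it appears only in the separate list after the table, without a frequency category.

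**The case against.** **The rules still function.** A reader might infer that the hepatic rules cannot work as written. The documents do not support that. Section 6.3 is conditional. Its ALT part runs on required data, and its AST and GGT parts apply, with printed cut-offs, whenever a result exists.

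**Section 5.4.1.1 does not demand screening.** It names the enzymes only to keep a transient Grade 3 value from counting as a DLT, and its trigger is general. This stands. The firm rules on AST and GGT are those in Section 6.3.

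**The narrow screen may be deliberate.** ALT with bilirubin is used consistently: in eligibility, the re-check, removal criterion (g) of Section 10.1, and the schedule. Appendix V also tells sites to obtain whatever further tests good care requires. That may explain the omission, but it does not remove the conflict. It leaves AST and GGT to site discretion, and Section 6.3 and Appendix XI still rely on them. The same Appendix V note says the list holds what the primary and secondary aims need, and tolerability is a secondary aim.

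**Missed liver harm is not shown.** A reader might infer a demonstrated safety gap. The documents give no rate of isolated AST or GGT elevation with normal ALT. In the adult liver-cancer study HCC1001, ALT and AST increases were each reported in 27.3% of subjects. This does not show that the same subjects were affected, but it is no evidence that ALT monitoring misses cases.

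**Little turns on it at study level.** There is one starting dose level, Section 11 has no toxicity stopping boundary, and the toxicity tables are descriptive. This is correct and limits the weight of the point.

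**Conclusion.** The inconsistency is real and moderate. Section 6.3 acts on three enzymes and Section 8.1 requires one. For AST and GGT, hold, removal and DLT classification depend on unscheduled testing, so toxicity ascertainment for aim 1.2.2 would be incomplete and could vary between sites. The recovery test also lacks an eligibility value and a required baseline for both. It would be tempting to read 150 U/L (3 × 50, the top of Grade 1) as an AST recovery limit by analogy with 135 U/L for ALT, but the protocol does not say so.

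The primary response endpoint and the decision rule of at least 3 responses in 20 are not affected.

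The conclusion rests on two things. First, no other study document requires these tests. The lettered key to the later-cycle map was not in the text available, and the case report form packet is separate, although the Section 8.1 column for later cycles agrees with the finding. Second, sites differ in how often they order AST and GGT. The documents do not describe this; it follows from leaving the choice to them.

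**What to change.** Reconcile Sections 4.1.7.3, 5.4.1.1, 6.3 and 8.1 with Appendices V and XI, so that every enzyme used in a hold, removal or DLT rule is also in the required schedule and has a stated baseline or recovery reference. How to bring the passages into line is for the clinical team to decide. Check the later-cycle key in Appendix V at the same time.

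For any enzyme not measured in all patients, the toxicity table should also show the number tested, so that its incidence can be read against the right denominator.

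The cost is wording, or at most two analytes on chemistry samples already drawn. No sample size, visit or analysis of response changes.

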- 1 Women of childbearing potential require a negative pregnancy test prior to starting treatment; sexually active patients must use an acceptable method of birth control. Abstinence is an acceptable method of birth control.
- 2 If patients have Grade 4 neutropenia then CBCs should be checked at least every other day until recovery to Grade 3 or until meeting the criteria for dose limiting toxicity.
- 3 If patients develop Grade 3 or greater thrombocytopenia then CBCs should be checked every 3 to 4 days until recovery per [Section 6.1](#).
- 4 Tumor Disease Evaluation should be obtained on the next consecutive cycle after initial documentation of either a PR or CR. Subsequent scans may restart 2 cycles after the confirmatory scan. If the institutional investigator determines that the patient has progressed based on clinical or laboratory evidence, he/she may opt not to confirm this finding radiographically.
- 4-A Neurological exam is also required for CNS patients.
- 4-B Non-Hodgkin Lymphoma/ Histiocytosis patients are required to have PET scans within 2 weeks prior to start of therapy and should also be followed with PET scans if positive at diagnosis. Refer to [Section 12.8](#).
- 4-C Patients with neuroblastoma must have both CT/MRI and MIBG scintigraphy prior to the start of therapy if the patient was enrolled with or has a history of having MIBG avid tumor. Otherwise the patient must have both CT/MRI and bone scan prior to the start of therapy. For patients with neuroblastoma and measurable disease by CT or MRI, lesions should be measured and followed using the same modality (CT or MRI) in addition to MIBG or bone scan. For patients with neuroblastoma and evaluable disease by MIBG scintigraphy or bone scan, use the same modality (MIBG scintigraphy or bone scan) to image and follow patients; CT/MRI are not required but may be performed as clinically indicated. Refer to [Section 12.5.4](#) and [Section 12.9](#).
- 5 Bone marrow aspirate and/or biopsy only required in patients suspected of having bone marrow metastasis on the basis of history, symptoms, laboratory evaluation or other clinical data.
- 6 Bone marrow aspirate and/or biopsy should be performed only when complete response or partial response is identified in target disease or when progression in bone marrow is suspected.
- 7 Medication diary (see [Appendix III](#)) should be reviewed weekly during cycle 1, after completion of each treatment cycle and uploaded into RAVE.

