### 8.3 Radiology Studies

#### 8.3.1 Bone Age/Knee MRI

All tibial radiographs and knee MRIs (if obtained) should be submitted for review.

8.3.2 Central Radiology Review for Response: Patients who respond (CR, PR) to therapy or have long term stable disease (SD) ( $\geq 6$  cycles) on protocol therapy will be centrally reviewed. The Operations center will notify the site when a patient has met the criteria for review. The tumor disease evaluations to be submitted for review include baseline (pre-study) evaluations as well as all end of cycle tumor disease evaluations which occurred while the patient was on the subprotocol therapy study.

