## 10.0 **CRITERIA FOR REMOVAL FROM PROTOCOL THERAPY AND OFF STUDY CRITERIA**

### 10.1 **Criteria for Removal from Protocol Therapy**

- a) Clinical (including physical examination or serum tumor markers) or radiographic evidence of progressive disease (See [Section 12](#)).
- b) Adverse Events requiring removal from protocol therapy (See [Section 6](#)).
- c) Refusal of protocol therapy by patient/parent/guardian
- d) Non-compliance that in the opinion of the investigator does not allow for ongoing participation.
- e) Completion of 26 cycles of therapy.
- f) Physician determines it is not in the patient’s best interest.

- g) Repeated eligibility laboratory studies (CBC with differential, bilirubin, ALT (SGPT) or serum creatinine) are outside the parameters required for eligibility prior to the start of protocol therapy (See [Section 8.1](#)).
- h) Study is terminated by Sponsor.
- i) Pregnancy
- j) Patient did not receive protocol treatment after study enrollment

**Patients who are removed from protocol therapy during cycle 1 should continue to have the required observations in [Section 8.1](#) until the originally planned end of the cycle or until all adverse events have resolved per [Section 13.4.4](#), whichever happens LATER. The only exception is with documentation of the patient's withdrawal of consent from the APEC1621SC screening protocol. Patients who are removed from protocol therapy in subsequent cycles should have the necessary observations to ensure adequate clinical care.**

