### 11.3 Study Design

The primary cohort will employ a single stage A'Hern design of N=20. The agent will be deemed worthy of further study in the relevant subset of patients (i.e. biomarker positive in any histology, biomarker positive in a particular histology, etc) if the decision rule is met. Operating characteristics are shown below.

Cohort	N	Decision Rule	Alpha	Power
Primary biomarker positive	20	≥ 3 responses	10%	90%

Histology-specific biomarker positive expansion cohorts will, by definition, be deemed worthy of further study, since they will have at least 3 responses. The table below shows 90% confidence intervals (Wilson method) for a range of observable response rates.

Cohort Size	Observed Response Rate	90% Confidence Interval
10	30%	13% - 56%
10	40%	19% - 65%
10	50%	27% - 73%

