#### 11.3.1 **Primary Cohort:**

APEC1621B will evaluate a primary cohort of 20 mutation-matched (“biomarker positive”) evaluable patients of any histology for the primary study aim of determining the objective response rate (CR/PR according to the response criteria in [Section 12.3](#)) to the agent. Using an A'Hern design with alpha=10%, a sample of N=20 will provide 90% power to detect an improvement in response rate from 5%, if the treatment is ineffective, to 25% if the targeted therapy is sufficiently effective to warrant further study. If there are at least 3 responses out of 20 in the primary cohort, the biomarker/therapy match will be deemed a success.

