#### 11.5 **Evaluability for Response**

Any eligible patient who is enrolled and receives at least one dose of protocol therapy will be considered evaluable for response. Any patient who receives non-protocol anti-cancer therapy during the response evaluation period will be considered a non-responder for the purposes of the statistical rule, unless they show an objective response prior to receiving the non-protocol anti-cancer therapy (in which case they will be considered a responder). Patients who demonstrate a complete or partial response confirmed by central review will be considered to have experienced a response. When opening expansion cohorts, the evaluation period for determination of best response will be the first 6 treatment cycles. All other patients will be considered non-responders. Patients who are not evaluable for response evaluation may be replaced for the purposes of the statistical rule. All patients considered to have a response (CR or PR) must have imaging studies reviewed centrally at the COG. Centers will be notified by the COG about requests for scans of patients with stable disease. Preliminary assessment of activity using institutionally provided tumor measurements will be entered into CDUS quarterly. The central review by COG will be provided as the final reviewed assessment of response when such becomes available.

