**12.4.3 Overall Response Assessment**

Table 1: For Patients with Measurable Disease (i.e., Target Disease)

Target Lesions	Non-Target Lesions	New Lesions	Overall Response	Best Overall Response when Confirmation is Required*
CR	CR	No	CR	≥ 28 days Confirmation
CR	Non-CR/Non-PD	No	PR	≥ 28 days Confirmation
CR	Not evaluated	No	PR	
PR	Non-	No	PR	

	CR/Non-PD/not evaluated			
SD	Non-CR/Non-PD/not evaluated	No	SD	documented at least once $\geq$ 28 days from baseline
PD	Any	Yes or No	PD	no prior SD, PR or CR
Any	PD**	Yes or No	PD	
Any	Any	Yes	PD	

* See RECIST 1.1 manuscript for further details on what is evidence of a new lesion.  ** In exceptional circumstances, unequivocal progression in non-target lesions may be accepted as disease progression.  Note: Patients with a global deterioration of health status requiring discontinuation of treatment without objective evidence of disease progression at that time should be reported as “symptomatic deterioration.” Every effort should be made to document the objective progression even after discontinuation of treatment.
				

Table 2: For Patients with Non-Measurable Disease (i.e., Non-Target Disease)

Non-Target Lesions	New Lesions	Overall Response
CR	No	CR
Non-CR/non-PD	No	Non-CR/non-PD*
Not all evaluated	No	not evaluated
Unequivocal PD	Yes or No	PD
Any	Yes	PD
* ‘Non-CR/non-PD’ is preferred over ‘stable disease’ for non-target disease since SD is increasingly used as an endpoint for assessment of efficacy in some trials so to assign this category when no lesions can be measured is not advised		

Table 3: Overall Response for Patients with Neuroblastoma and Measurable Disease

CT/MRI	MIBG	Bone Scan	Bone Marrow	Catechol	Overall
PD	Any	Any	Any	Any	PD
Any	PD	Any	Any	Any	PD
Any	Any	PD	Any	Any	PD
Any	Any	Any	PD	Any	PD
SD	CR/PR/SD	Non-PD	Non-PD	Any	SD
PR	CR/PR	Non-PD	Non-PD	Any	PR
CR/PR	PR	Non-PD	Non-PD	Any	PR
CR	CR	Non-PD	Non-PD	Elevated	PR
CR	CR	CR	CR	Normal	CR

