**12.9.1 Evaluation of Best Overall Response**

The best overall response is the best response recorded from the start of the treatment until disease progression/recurrence (taking as reference for progressive disease the smallest measurements recorded since the treatment started). The patient's best response assignment will depend on the achievement of both measurement and confirmation criteria.

Table 5. Sequences of overall response assessments with corresponding best response.

1st Assessment	2nd Assessment	Best Response
Progression		Progressive disease
Stable, PR, CR	Progression	Progressive disease
Stable	Stable	Stable
Stable	PR, CR	Stable
Stable	Not done	Not RECIST classifiable
PR	PR	PR
PR	CR	PR
PR, CR	Not done	Not RECIST classifiable
CR	CR	CR

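### The confirmatory scan is scheduled by treatment cycle, so a responder who stops erdafitinib before it may stay unconfirmed, and the plan gives two answers on how that patient counts

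*Combined protocol and SAP*

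**What the plan says.** **When the second scan is due.** Section 8.1, footnote 4: "Tumor Disease Evaluation should be obtained on the next consecutive cycle after initial documentation of either a PR or CR". Section 12.3 ties the confirmatory scan to the next cycle in the same way.

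**What happens after drug stops.** For removal after cycle 1, section 10.1 says: "Patients who are removed from protocol therapy in subsequent cycles should have the necessary observations to ensure adequate clinical care". Section 10.2 keeps the patient on the subprotocol for 30 days and specifies adverse-event follow-up for that period; the patient then passes to the screening protocol, APEC1621SC. Section 8.3.2 asks sites to submit for central review the baseline scans and "all end of cycle tumor disease evaluations which occurred while the patient was on the subprotocol therapy study".

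**How response is scored.** Section 11.4 defines a responder by a best response of PR or CR. Section 12.9 requires two determinations at least 3 weeks apart for either. In Table 5 (12.9.1), a PR or CR whose second assessment was not done cannot be classified under RECIST. Section 11.5 keeps every eligible patient with one dose evaluable, describes a responder as one whose CR or PR is confirmed by central review, and adds: "All other patients will be considered non-responders". Section 12.3.1.1 has similar central-review wording. Neither 11.5 nor 12.3.1.1 mentions a second scan.

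**How long assessments count.** Section 12.9.1 takes the "best response recorded from the start of the treatment until disease progression/recurrence", so the window does not close at the last dose.

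**The concern.** The endpoint runs to progression, but the scan that confirms it is scheduled by cycle. A patient with a first PR or CR who is then taken off erdafitinib for toxicity, without progression and without other anti-cancer therapy, has no next cycle to attach the scan to. Section 6 provides for such removals, for example when toxicity does not resolve within 14 days or after Grade 4 ALT/AST/GGT. In the smallest BSA band, Appendix IV shows removal from protocol therapy in place of a reduced dose.

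For progression, the plan does pursue information off drug. The note to Table 1 in 12.4.3, on patients who stop because of global deterioration in health, says: "Every effort should be made to document the objective progression even after discontinuation of treatment". There is no matching instruction for confirming a response. Any gap therefore removes responses and never adds them.

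The success rule needs only three responders. A response lost because drug was stopped for toxicity, rather than for want of activity, could decide the primary cohort. It could also decide whether a histology-specific expansion cohort opens, since 11.3.2 again needs three. Whether the response is lost would depend on local scanning practice.

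**Working it through.** **1. The plan's own figures.** Section 11.3: "The primary cohort will employ a single stage A'Hern design of N=20". Section 11.3.1 gives a null rate of 5%, a target rate of 25%, success at 3 or more responses, alpha 10% and power 90%. With X binomial (n = 20, p):

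- Type I error = P(X ≥ 3 | p = 0.05) = 7.55%, inside the 10% limit. A threshold of 2 would give 26.4%.
- Power = P(X ≥ 3 | p = 0.25) = 1 − (0.75^20 + 20 × 0.25 × 0.75^19 + 190 × 0.25² × 0.75^18) = 90.9%.

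The design reproduces.

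**2. Which patient is affected.** Tumor evaluation is every other cycle at the start (8.1), so a response found on schedule appears no earlier than the end of cycle 2. The confirmatory scan is due one 28-day cycle later. A patient who stops in that interval comes under the later-cycle sentence of 10.1, not its fuller cycle 1 requirement.

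**3. The two scoring routes for that patient, if no second scan is done.**

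| Route | Sections | Result |
|---|---|---|
| Best response | 12.9 (two determinations), Table 5 (unclassifiable), 11.4 (responder needs PR or CR), 11.5 default | Non-responder, still in the denominator |
| Central review | 11.5 and 12.3.1.1 (CR or PR upheld centrally, no second scan named) | Could be read as responder |

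The first route is the more natural reading, because 12.9.1 makes best response depend on confirmation as well as measurement. The second is not excluded.

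**4. Size on the first route.** Let q be the share of true responders who stop after the first PR/CR and have no second scan counted. The documents give no value for q. The effective response rate is p(1 − q), with the same exact rule. The last column is the chance that at least one of exactly three true responders is lost, 1 − (1 − q)³.

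| q (assumed) | 0.25(1 − q) | Power | Type I error | Reversal with exactly 3 responders |
|---|---|---|---|---|
| 0 | 0.2500 | 90.9% | 7.55% | 0 |
| 2% | 0.2450 | 90.0% | 7.2% | 5.9% |
| 5% | 0.2375 | 88.7% | 6.7% | 14.3% |
| 10% | 0.2250 | 86.1% | 5.9% | 27.1% |
| 13% | 0.2175 | 84.3% | 5.4% | 34.1% |

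The two largest values come from adult data in section 2.2 (Study BLC2001): a stated 10% stopping for adverse events, and 13 of 99 (13.1%) in the 8 mg/day group. Both cover all of treatment and all patients, whereas q concerns responders in about one cycle. They are ceilings.

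**5. Reading the last column.** At a true rate of 25%, exactly three responders in 20 occurs with probability 13.4%. The last column is conditional on that event.

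**The case against.** A reader might infer that a responder who stops drug early is, as a settled matter, scored a non-responder. The documents do not support that. Section 12.9.1 counts assessments up to progression, so an off-drug scan is permitted, and 12.9 asks for only 3 weeks between determinations. If such a scan is done, the Table 5 row for a missing second assessment does not apply. A scan within the 30-day follow-up of 10.2 is arguably still on the subprotocol for 8.3.2. Table 5 itself stops at unclassifiable; only the 11.5 default turns that into non-response. The central-review wording in 11.5 and 12.3.1.1 points the other way. The APEC1621SC follow-up schedule is not part of these documents and may include imaging. All of this stands, and it limits the point to what may happen.

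A reader might also infer that such removals are likely. The documents give no rate for the relevant interval. Most dose-limiting toxicities lead first to a hold, with possible resumption at a lower dose, and in the adult 8 mg/day group 55 patients needed a reduction while 13 stopped for adverse events.

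The calculation is also unfavorable to the plan. It assumes that none of the affected patients is scanned and that all would have confirmed. If q = 5% and half are scanned anyway (assumption), the effective q is 2.5% and power is 89.8%. Requiring confirmation among all dosed patients is a conservative choice, and if the 25% target already means confirmed response in that population, part of the loss is already in the design.

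What remains is that no sentence requires the scan off drug, none clearly collects it, and the scoring of a patient without it can be read both ways.

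**Conclusion.** The point holds as a gap in scheduling and an unreconciled scoring rule. It does not show that responses will be lost. Under the more natural reading, an early-stopping responder without a second scan counts as a non-responder; under the central-review wording the same patient could count as a responder.

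The bias goes in one direction: the observed response rate and power fall, and type I error falls with them. It is probably small. With q assumed at 2% to 5%, power drops by 0.8 to 2.2 points, and it stays at or above 90% up to about q = 2%. The 84.3% at q = 13% is a ceiling, and the 34.1% reversal figure combines that ceiling with the case of exactly three true responders; neither should be quoted as the expected effect. The reason to act is the low threshold: at exactly three responders one missing scan reverses the decision, and the remedy is cheap.

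**What to change.** - **8.1 footnote 4 and 12.3:** set the confirmatory tumor evaluation at the date on which the next cycle's evaluation would have fallen after the first PR or CR, whether or not the patient is still taking erdafitinib. Except only progression, other anti-cancer therapy, and withdrawal of consent.
- **8.3.2:** add that scan to the set submitted for central review.
- **11.5 and 12.3.1.1 against 11.4, 12.9 and Table 5:** state once how an unconfirmed PR or CR is scored, and use that rule throughout. At the same time reconcile the confirmation interval, which is at least 28 days in Table 1 of 12.4.3 and at least 3 weeks in 12.9.

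The cost is a few sentences in an amendment. The sample size, decision rule and treatment plan do not change. A confirmatory scan is already planned for responders, so the change re-anchors it to a date. The downside is that a few early-stopping responders have one planned scan off drug. The change recovers only responses that would have confirmed, so power returns to 90.9% only if all of them would have.
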